8. CORRELATIVE/SPECIAL STUDIES: CLOSED TO ADDITIONAL SAMPLE COLLECTIONS

8.1. Correlative Objective

Changes in inflammation blood markers at 3, 6, 9 and 12 months after radiation therapy when compared to baseline. Plasma TGF- β 1 will be measured by molecular specific Enzyme Linked Immune Sandwich Assay (ELISA). The levels of plasma cytokines will be measured by ready to use kits for the concentrations of 29 proinflammatory cytokines, including G-CSF, IL-1 α , IL-1 β , IL-1ra, IL-6, IL-8, IP-10, MCP-1, MIP-1, TGF- α , and TNF- α .

8.2. Correlative lab study

Patients will be offered the opportunity to participate in the correlative components of the study, however participation will be optional. Whole blood, plasma, and serum samples will be drawn within 2 weeks prior to radiation therapy and then drawn 3, 6, 9 and 12 months after radiation therapy.

Platelet-poor plasma will be obtained for cytokine assays; serum samples will be used for, cell death assays and other markers as indicated; buffy coat will be used for genomic studies including methylation analysis. Plasma TGF- β 1 will be measured by molecular specific Enzyme Linked Immune Sandwich Assay (ELISA). The levels of plasma cytokines will be measured by ready to use kits, such as LINCOPlex (microsphere-based sandwich immunoassay) for the concentrations of 29 proinflammatory cytokines, including G-CSF, IL-1 α , IL-1 β , IL-1ra, IL-6, IL-8, IP-10, MCP-1, MIP-1, TGF- α , and TNF- α . RILT will be diagnosed and graded based on CTCAE 4. For genomic studies, we will focus our efforts on (but not limited to) global SNP and DNA methylation as well as SNP and methylation analysis of TGF β 1, tissue plasminogen activator (tPA) and angiotensinconverting enzyme (ACE), which are associated with radiation-induced thoracic toxicity such as radiation induced lung injury. Genetic variations within functional locus of these genes will be assessed for in each patient by using gene specific PCR technology. Such SNP studies will be performed using polymerase chain reaction (PCR) and allele specific primers. Genome wide methylation profiling will be performed using the Illumina Infinium HumanMethylation450 BeadChip array which examines the methylation status of 485,577 CpG sites distributed throughout the whole genome, covering 96% of CpG islands and 99% of RefSeq genes. Methylation status of select genes of interests will also be validated using pyrosequencing. Bioinfomatic methodology may be applied for data analysis. Blood markers (cytokine and genomics)

during early course of treatment will be correlated to clinical outcome including tumor control.

Blood (whole blood, plasma and serum) will be processed by the UWCCC BioBank (Translational Science BioCore). 30 ml peripheral blood (two 10 ml EDTA tubes and one 10 ml SST tube) will be taken from each patient at each time point.

Blood—Plasma: 10 ml of blood will be collected in one EDTA (purple top) tube twice. Blood will be inverted 6-7 times to ensure adequate mixing with anticoagulant, then centrifuged within one hour of collection in a standard clinical centrifuge at 3000g at 4°C for 10 minutes. If the interval between specimen collection and processing is anticipated to be greater than one hour, the specimens are kept on ice until centrifuging can begin. Samples will be carefully pipetted in up to ten 1.5 ml cryovials as 1.0 ml aliquots of plasma. Care will be taken to avoid pipetting any blood cells or buffy coat (red/white blood cells). Plasma samples will be labeled and cryovials will be stored at -80°C.

Blood—Serum: 10 ml of blood will be collected without coagulants in one SST (red top) tube. Blood will sit at room temperature for 30 min to allow clot formation, then centrifuged in a standard clinical centrifuge at 3000g at 4°C for 10 minutes. Samples will be transferred into up to ten 1.5 ml cryovials as ~1ml aliquots of separated serum. Serum samples will be labeled and cryovials will be stored at -80°C.

Blood—Whole Blood: 10 ml of blood will be collected in one EDTA (purple top) tube. Blood will be inverted 6-7 times to ensure adequate mixing with anticoagulant and then carefully pipetted into three to five 1.5 ml cryovials as 0.5 ml aliquots of whole blood. Samples will be labeled and cryovials will be stored at -80°C.

Initial collected specimens will be labeled with the patient name, date, time and time point collected. A completed specimen collection flow sheet will accompany each specimen.

In an effort to protect the patient's identity in the laboratory, the stored frozen samples will be identified by a code that can be linked back to the patient by the investigators, but not other laboratory personnel.

Blood collections will be scheduled at baseline, which will be within 2 weeks of radiation therapy beginning, and then 3 months, 6 months, 9 months, and 12 months after the completion of radiation therapy.

8.3. Correlation with daily localization imaging

Images acquired for daily localization may show changes in lung tissue that occur during therapy. These images may also be investigated as described in secondary endpoints (Section 10.2)

9.

STUDY CALENDAR

	Pre study ¹	Simulation	Weekly during Rt	3 mo post	6 mo post	12 mo post

H & P	X			X	X	X
KPS	X		X	X	X	X
Weight	X		X	X	X	X
Informed Consent	X					
4DCT		X³		X	X	X
PFT's ² and pt self assessment		X⁴		X⁵	X⁵	X⁵
Toxicity Assessment	X		X	X	X	X

10. MEASUREMENT OF EFFECT

The aims of this proposal are to use quantitative imaging to characterize pulmonary biomechanics, improve pulmonary function following RT by utilizing per-RT pulmonary function data to avoid regions of the lung with high function, and gather outcomes data to further refine our radiation dose response model. The primary endpoint is changes in pulmonary function, based on changes in tissue elasticity measured from 4DCT. Secondarily we will evaluate global measures of change using routine pulmonary function tests.

10.1. Primary endpoint

Lung tissue elasticity changes. The primary endpoint of this study will be the ratio of the tissue elasticity map following RT to the elasticity map before RT (i.e., the Jacobian ratio of (post RT /pre RT)) calculated from 4DCT at 3 months post-RT. Based on the randomness of our measurement technique, diminished expansion (i.e. substantial change) is defined as a Jacobian ratio <0.94 (i.e., less than 94% of the pre-RT value).

10.2. Secondary endpoints

10.2.1. Lung tissue elasticity changes

Temporal changes in reduced elasticity. Since the differences in expansion may increase with time, we will investigate these same changes during therapy (using localization images acquired per 5.4) and at 6 and 12 months post-RT.

10.2.1.1. Temporal changes in increased elasticity. At 3, 6 and 12 months post-RT we will determine the volume of lung where expansion is improved (Jacobian ratio (post-RT/pre-RT) > 1.06)

10.2.1.2. Temporal changes in fraction of expanding lung. At 3, 6 and 12 months post-RT we will determine the volume of lung where “meaningful” expansion occurs (Jacobian post-RT > 1.1).

10.2.1.3. Validation of dose response model. Validation in consistency of tissue elasticity changes measured with values predicted based on existing radiation dose response curves.

10.2.2. Global measures of change

10.2.2.1. Pulmonary Function Tests. Changes in patient self-assessment, forced vital capacity (FVC), forced expiratory volume in one second (FEV1), and diffusion lung capacity for carbon monoxide (DLCO). All metrics will be evaluated at 3, 6, and 12 months post-RT in comparison to values pre-RT.

10.2.2.2. Inflammation. Plasma TGF- β 1 will be measured by molecular specific Enzyme Linked Immune Sandwich Assay (ELISA). The levels of plasma cytokines will be measured by ready to use kits for the concentrations of 29 proinflammatory cytokines, including G-CSF, IL-1 α , IL-1 β , IL-1ra, IL-6, IL-8, IP-10, MCP-1, MIP-1, TGF- α , and TNF- α .

10.2.3. Repeatability of 4DCT based measures of lung tissue elasticity

10.2.3.1. Variation of the tissue elasticity calculated between scan 1 and scan 2 at each time point will be quantified and compared to longitudinal changes in tissue elasticity.

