1.2. Secondary Objectives

1. Characterize and correlate temporal changes in lung tissue elasticity with delivered radiation doses to anatomical and functional regions within the thorax.
2. Quantify global changes following radiation therapy (RT) for lung cancer, including those observed from Pulmonary Function Tests (PFTs) and inflammation markers in blood plasma for subjects who voluntary consent to provide their blood. These too will be correlated with the delivered radiation doses to anatomical and functional regions within the thorax, and with the maps of post-radiation therapy changes in lung tissue elasticity.
3. Quantify the repeatability of 4DCT based measures of lung tissue elasticity to demonstrate the changes following radiation therapy are greater than the expected variation from the procedure itself and determine the expected variance in longitudinal studies.

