5.2. Baseline Research Assessments

- 5.2.1. **4DCT.** This is ordered in addition to the standard 4DCT performed for RT-simulation
- 5.2.2. **Patient self-assessment.** Assessment is based on a modified Borg scale, which has a history of use in pulmonary labs, with a scale of 1 (resting comfortably in a chair with no effort) to 10 (the most exertion and difficult breathing ever experienced)
- 5.2.3. **RTOG defined acute toxicity evaluation.** Evaluate both lung and esophageal toxicity (Appendix B)
- 5.2.4. **RTOG late toxicity evaluation.** Evaluate lung, esophageal, skin, subcutaneous tissue, spinal cord, heart, and bone (Appendix C)
- 5.2.5. **Constitutional assessment:** quantify nausea, vomiting, diarrhea and other symptoms prior to initiating chemoradiation and any medications used for these symptoms

5.3. 4-Dimensional Computed Tomography (4DCT) Imaging

4DCT imaging is performed at simulation (treatment planning) in all patients. This first 4DCT is clinically indicated for radiation simulation as a standard procedure. This clinical imaging data will also be used for research in this protocol to evaluate the biomechanical tissue elasticity of the lungs. Lung tissue elasticity is being used as a surrogate for ventilation, which in turn is a component of pulmonary function. Because the goal of the research arm is to reduce pulmonary function damage, changes in lung tissue elasticity will be quantified using 4DCT and it's essential the changes observed be distinguished from random changes in our measurement. Consequently, each subject will receive two 4DCT scans at each time point in order to quantify the repeatability of the measure of tissue elasticity and to demonstrate the changes following RT are greater than the expected variation from the procedure itself. The results from both 4DCT scans will

be used by taking the geometric mean of the tissue elasticity measures of scan 1 and scan 2 at each time point.

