Subjects will undergo a total of 7 research-ordered 4DCT scans: one at simulation, and two scans at each of the 3 post-radiation therapy time points (3, 6, and 12 months). Each 4DCT scan delivers approximately 75 mSv, which is the average value observed over 10 patients in our clinic using the newly installed Siemens Edge scanner. The Background Equivalent Radiation Time (BERT) is 25 years for each 4DCT scan, where the background radiation is assumed to be 3 mSv per year. To place this radiation exposure into further context, the radiation dose from the 7 research-ordered 4DCT scans (0.53 Gy) represents less than 1% of the radiation dose the patient will receive from their radiation therapy treatments. In an effort to make the radiation doses from the 4DCT scans “as low as reasonably achievable,” the radiation dose subjects receive for each 4DCT scan has recently been reduced by 2-3 times LOWER than prior care at UWHC. This reduction has been made possible by the improved radiation detection technology on the Siemens Edge CT scanner in Radiation Oncology. If further dose reduction can be accomplished by additional technologies or software development, these too will be implemented.

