5.7. Study Procedures and Walkthrough

- 5.7.1. **Radiation therapy planning simulation.** RT simulation will consist of 4DCT imaging as per Department of Human Oncology's standard of care. A second research 4DCT will be acquired at this time point.
- 5.7.2. **Pulmonary function tests.** The subject will be sent to the pulmonary function lab for spirometry, and DLCO. The pulmonary function tests may be done on the same day, but must be completed before the subject receives the first fraction of radiation therapy.
- 5.7.3. **Dosimetric planning.** Performed according to standard of care.
- 5.7.4. **Treatment.** Subjects will be treated once daily or every other day if receiving SBRT. The respiratory surrogate systems will be used daily during radiation therapy treatment per standard clinical practice to monitor respiratory motion.
- 5.7.5. **Post-treatment 4DCTs.** Three more 4DCT imaging sets will be obtained, at 3 months, 6 months, and 12 months after the last radiation treatment (10 week window: – 2 weeks/+8weeks). These 4DCT must be performed on the Radiation Oncology Siemens Edge. These are research-designated 4DCTs and will not be used for clinical care.
- 5.7.6. **Post-treatment PFT.** Subjects will undergo PFT at the 3 month, 6 month, and the 12 month imaging to obtain spirometric, and DLCO measurements. These will be performed for research purposes.
- 5.7.7. **Follow-up.** Subjects will have follow-up appointments with their radiation oncologist every 3 months for the first year, every 4 months for year two, and every 6 months for years 3-5. Follow-up mirrors that of RTOG-0117, enabling time-point comparisons. Data to be collected are outlined in section 11 (measurement of effect). The follow-up time points are consistent with standard of care post radiation disease monitoring.

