6. DOSING DELAYS/DOSE MODIFICATIONS

Not applicable. If radiation dose needs to be modified or delayed, this is per standard of care and beyond the scope of this study. A note will be made in the study chart regarding any changes to radiation dose and any breaks in radiation therapy.

7. ADVERSE EVENTS:

The risks of harm for those subjects randomized to the research arm (arm 2) is equivalent to the control arm: optimized treatment plans in the research arm will be designed to meet the same dose specifications to organs-at-risk. In other words, when comparing the control and research arm:

- the same radiation doses will be delivered to the tumors
- the same radiation dose limits will be achieved for all normal tissues

There are minimal additional risks associated with the research procedures of 4DCT and PFT's.

The most significant risk from 4DCT is the increased radiation exposure which will be less than 1% of the dose received from the prescribed radiation therapy. Subjects may experience

discomfort from laying on their back during additional 4DCT scans. Each 4DCT scan will last 90 seconds. It is anticipated that patients will spend approximately 10-15 minutes on their back to position and collect the scans.

PFT's have the following associated risks: the test requires subjects to breathe in and out quickly, which may cause them to feel dizzy or faint. The test may increase the risk of asthma attack in those with asthma. In very rare cases, PFTs may cause a collapsed lung.

Patients will receive standard of care therapeutic radiation therapy dosing as part of this study. Toxicities associated with therapeutic radiation include: Reversible or permanent alopecia, bone marrow toxicity, skin reactions, and esophagitis are expected side effects of radiation therapy. Radiation-induced myocarditis or transverse myelitis rarely occur at doses lower than 50 Gy. Radiographic evidence of radiation change and subsequent fibrosis of the lung will occur within lung volume receiving first 6-12 months after initiation of treatment.

Acute (within 90 days post RT completion) and late radiation toxicities (> then 90 days post RT completion) will be recorded with special attention to the toxicities listed in appendix B and C. Any treatment interruption will be based on treating physician judgement and be documented as part of the study toxicity assessments.

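### Objective 3 asks for a longitudinal variance, but the planned scan 1/scan 2 comparison measures only within-session repeatability

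*Combined protocol and SAP*

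**What the plan says.** Section 1.2, secondary objective 3, has two parts. The first is to show that "changes following radiation therapy are greater than the expected variation from the procedure itself". The second is to "determine the expected variance in longitudinal studies".

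Section 5.3 provides the replication: "each subject will receive two 4DCT scans at each time point in order to quantify the repeatability of the measure of tissue elasticity". It also says that the two scans at a time point are combined by geometric mean. For baseline, section 5.7.1 adds the repeat to the simulation visit: "A second research 4DCT will be acquired at this time point". The post-radiation pairs come at 3, 6 and 12 months.

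The timing appears in the risk text of section 7, which gives 90 seconds per scan and adds: "It is anticipated that patients will spend approximately 10-15 minutes on their back to position and collect the scans".

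The analysis is one sentence in section 10.2.3.1: "Variation of the tissue elasticity calculated between scan 1 and scan 2 at each time point will be quantified and compared to longitudinal changes". It names no statistic, model or limit. Section 11 adds nothing on between-visit variance.

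**The concern.** Two scans taken minutes apart share the day and the patient's clinical condition, and probably the set-up. Their difference reflects scan-level noise. A change from before radiation to three or more months afterwards also carries whatever differs between visits: positioning, habitual breathing pattern, intercurrent illness, and registration across months. Averaging two scans within a visit reduces the scan noise but leaves the visit component untouched.

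If the scan 1/scan 2 figure is the only yardstick, visit-to-visit variation can be mistaken for change beyond the noise of the method. The second half of objective 3 also has no analysis that can answer it, however large or small the visit variation is. A later study that took the within-session figure as its longitudinal variance could be wrongly sized.

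**Working it through.** **Inputs.** Scan counts and timing are from sections 5.3, 5.7.1 and 7. The geometric-mean rule is from section 5.3. No document gives s or v, so v/s is an assumption, shown from 0 to 2.

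**Step 1: what is replicated.** The stated seven research scans reproduce: 1 + 2 × 3 = 7. Adding the clinical simulation scan gives 8 = 4 time points × 2 scans. There is one pre-radiation time point and no untreated group. The scan component can be estimated from the pairs. The visit component is not in the pair differences, and in a pre/post difference it cannot be separated from radiation change.

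**Step 2: variances.** Take the log Jacobian as truth + visit error (SD v) + scan error (SD s), all independent, with the same variances at each visit.

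- Scan 1 minus scan 2, same visit: the visit error cancels, leaving s² + s² = 2s².
- Geometric mean of two scans at one visit: error variance v² + s²/2.
- Post/pre log ratio of two such means with no radiation effect: 2(v² + s²/2) = s² + 2v².

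The within-session part of the last quantity is s². That is half the raw scan-rescan variance, so it is the correctly scaled within-session yardstick.

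**Step 3: which way the error runs.** Against raw scan-rescan variation, s² + 2v² > 2s² requires v² > s²/2, that is v/s > 0.71. Against the scaled yardstick, s² + 2v² > s² holds for any v > 0.

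**Step 4: size.** With normal errors and r = v/s, the share of no-effect changes outside a nominal 5% limit is 2[1 − Φ(1.96/√(1 + 2r²))] for the scaled limit and 2[1 − Φ(1.96√2/√(1 + 2r²))] for the raw limit.

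| v/s (assumed) | No-effect variance | ÷ raw 2s² | ÷ scaled s² | Outside scaled limit | Outside raw limit |
|---|---|---|---|---|---|
| 0 | 1.0 s² | 0.5 | 1.0 | 5.0% | 0.6% |
| 0.5 | 1.5 s² | 0.75 | 1.5 | 11.0% | 2.4% |
| 0.71 | 2.0 s² | 1.0 | 2.0 | 16.6% | 5.0% |
| 1 | 3.0 s² | 1.5 | 3.0 | 25.8% | 11.0% |
| 2 | 9.0 s² | 4.5 | 9.0 | 51.4% | 35.6% |

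Both the direction and the size depend on v/s and on a scaling that section 10.2.3.1 does not state.

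**The case against.** **The first half of objective 3 can be met.** Read narrowly, variation from the procedure itself is what a scan-rescan pair measures, and section 10.2.3 is already headed as repeatability. This stands. The gap is in the second half, and in using the pair as the yardstick for change across months.

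**A single session is inferred.** No section uses those words or says whether the patient is repositioned between scans. The timing in section 7 makes one short session the natural reading, but it remains a reading. Breathing and registration can also differ between scans minutes apart, so part of what is called visit variation may already lie in s. That bears on the size of v, but the pair still contains no variation between visits.

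**The direction is not fixed.** A reader might infer that the comparison must overstate change. The documents do not support that. With raw scan-rescan variation set against two-scan means, the comparison is conservative when v/s is below 0.71, and no scaling is specified. Section 10.2.3.1 also does not say that any excess will be attributed to radiation.

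**The cut-offs.** A reader might infer that a within-session figure would be used to support the 0.94 and 1.06 cut-offs. Sections 10.1 and 11.1 tie 0.94 to measurement randomness, but they do not say whether that randomness was within or between sessions. No section says objective 3 will validate either value.

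**Any remedy from existing scans is imperfect.** All the repeat visits follow radiation. Section 10.2.1 allows that differences may grow with time, and section 2.2 describes loss of function outside the treated region. This stands and limits what the remedy can claim.

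**Conclusion.** The point holds in a limited form. The planned comparison estimates within-session repeatability, omits visit-to-visit variation, and so cannot deliver the longitudinal variance that objective 3 promises. It may overstate how far post-radiation change exceeds measurement variation, by an amount it cannot itself show. For illustration, at v = s the no-effect variance is 1.5 times the raw scan-rescan variance and 3 times the scaled one; at v = 0 the factors are 0.5 and 1. These rest on assumed v/s, independent errors with constant variances, and the single-session reading.

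The effect is confined to a secondary objective. One might infer that the primary result is compromised, but visit noise falls on both randomized arms. It adds variance to the arm comparison and does not by itself bias it. The point changes no printed figure. It is worth correcting because the stated method does not answer a stated objective and the correction is cheap.

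**What to change.** In section 10.2.3.1:

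1. Report the scan 1/scan 2 result as within-session repeatability. When setting it against longitudinal change, scale it to two-scan geometric means (s² for a post/pre log ratio, not 2s²). Do not use it alone as the longitudinal yardstick.
2. Add a variance-components model with subject, visit and scan terms, fitted to the individual scan maps at 3, 6 and 12 months in a pre-specified lowest-dose lung region.
3. Compare post-radiation change with scan plus visit variance, s² + 2v² for the post/pre log ratio of two-scan means.
4. State that the visit component applies to that region and includes any evolving radiation change there. It is therefore likely to be too large for that region, and it is not a strict upper bound for all lung.

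In section 1.2, limit the longitudinal-variance claim of objective 3 to what this model supports. If the model is declined, steps 1 and the narrowed objective would still correct the text.

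The cost is one extra analysis, edits to two sections and a repeatability figure that is likely to look less favourable. No further scans or radiation exposure are needed.
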